- The full analysis set (FAS) comprises all patients who are assigned to receive study treatment as per the intent-to-treat (ITT) principle, regardless of whether or

not they subsequently go on to receive study treatment or whether they deviate from the protocol in any major way.

- The modified intent-to-treat (mITT) set comprises all patients who are assigned to receive study treatment and have at least 1 post-baseline efficacy assessment (RECIST 1.1), even if they deviate from the protocol in any major way. The mITT will also include any patient that goes off study treatment because of clinical progression prior to the first scheduled per-protocol scan.
- The safety analysis set comprises all patients who receive any amount of study drug.
- The per-protocol set (PPS) comprises all patients who are assigned to receive study treatment, receive at least 1 injection of study treatment, have at least 1 post-baseline efficacy assessment (RECIST 1.1), and do not deviate from the protocol in any major way

All efficacy analyses will be based on the FAS and will also be conducted on the mITT set and PPS for exploratory purposes. The study's primary objective will be judged on the basis of the analysis of ORR. For CRC patients, only those with MSS and MSI-L will be included in the primary efficacy analysis. The safety analyses will be based on the safety analysis set and will group patients according to treatment actually received. Secondary and exploratory efficacy analyses will be performed on the FAS as well as on the mITT set and PPS for exploratory purposes.

Analysis of Primary Efficacy Endpoint: For each tumor-specific cohort, a Bayesian approach with non-informative

Jeffreys prior beta distribution with parameters $a = 0.5$ and $b = 0.5$ will be used to estimate the ORR (or CR/CRi/CRp rate in AML) and its 95% credible interval based on the posterior distribution.

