At the time of analysis, within each tumor-specific cohort, the prior distribution will be updated with all available data from the evaluable patients to obtain the posterior distribution of the true ORR. The posterior probabilities that ORR (or CR/CRi/CRp rate in AML) exceeds TV and LRV will be reported for each cohort. A high posterior probability that $ORR > LRV$ will support a “Go” decision to continue development in the cohort, and a low posterior probability that $ORR > TV$ will support a “Stop” decision to halt development in the cohort. A “Consider” decision results if neither a Stop nor a Go decision can be made. The specific criteria for making a Stop, Consider, or Go decision within each tumor-specific cohort are derived using the following acceptable risks:

- 10% false stop risk: maximum acceptable probability that $ORR > TV$ given that a Stop decision is made.
- 20% false go risk: maximum acceptable probability that $ORR \leq LRV$ given that a Go decision is made

Before reaching the planned sample size in a cohort, the posterior probabilities will be updated continuously after each patient (or group of patients) and will be used to determine, within each cohort, the predictive probability of eventually reaching a Stop decision at the planned sample size. If this predictive probability is $\geq 80\%$, then enrollment in that cohort may be stopped early for futility.

Stop/Go and futility decision criteria are non-binding and may be regarded as guidance and information to be integrated with a full medical review of safety and efficacy data observed at the time of analysis in determining the next course of action. No tests of statistical significance are planned.

CRC

Given a sample size of 20 patients in the CRC (third/fourth line) group, where TV = 20% and LRV = 10%, the decision criteria are as follows: Go if ≥ 4 responses observed (20%); Stop if ≤ 1 responses observed (5%). With these criteria, there is a 59% probability of a Go decision and 7% probability of a Stop decision if the true ORR is 20%, and there is a 13% probability of a Go decision and 39% probability of a Stop decision if the true ORR is 10%.

OvC

The same sample size, TV, LRV, decision criteria, and probability statements as the CRC group apply.

SCLC

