7.5. Analysis Sets

- The full analysis set (FAS) comprises all patients who are assigned to receive study treatment as per the ITT principle, regardless of whether or not they subsequently go on to receive study treatment or whether they deviate from the protocol in any major way.

- The modified intent-to-treat (mITT) set comprises all patients who are assigned to receive study treatment and have at least 1 post-baseline efficacy assessment (RECIST 1.1), even if they deviate from the protocol in any major way. The mITT will also include any patient that goes off study treatment because of clinical progression prior to the first scheduled per-protocol scan.
- The safety analysis set comprises all patients who receive any amount of study drug.
- The per-protocol set (PPS) comprises all patients who are assigned to receive study treatment, receive at least 1 injection of study treatment, have at least 1 post-baseline efficacy assessment (RECIST 1.1), and do not deviate from the protocol in any major way.

All efficacy analyses will be based on the FAS and will be conducted on the mITT set and PPS populations for exploratory purposes. For CRC patients, only those with MSS and MSI-L will be included in the efficacy primary analysis. The safety analyses will be based on the safety analysis set and will group patients according to treatment actually received. Secondary and exploratory efficacy analyses will be performed on the ITT/FAS as well as on the mITT and PPS populations for exploratory purposes.

Major protocol deviations will be defined in more detail in the study statistical analysis plan (SAP), and may include, but not be limited to, incorrect diagnosis and poor compliance.

All analyses using the PPS will group patients according to treatment actually received.

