7.6.1. Analysis of Primary Efficacy Endpoint

For each tumor-specific cohort, a Bayesian approach with non-informative Jeffreys prior beta distribution with parameters $a = 0.5$ and $b = 0.5$ will be used to estimate the ORR and its 95% credible interval based on the posterior distribution.

At the time of analysis, within each tumor-specific cohort, the prior distribution will be updated with all available data to obtain the posterior distribution of the true ORR. The posterior probabilities that ORR exceeds TV and LRV will be reported for each cohort. A high posterior probability that $ORR > LRV$ will support a “Go” decision to continue development in the cohort, and a low posterior probability that $ORR > TV$ will support a “Stop” decision to halt development in the cohort. A “Consider” decision results if neither a Stop nor a Go decision can be made. The specific criteria for making a Stop, Consider, or Go decision within each tumor-specific cohort are derived using the following acceptable risks:

- 10% false stop risk: maximum acceptable probability that $ORR > TV$ given that a Stop decision is made.

- 20% false go risk: maximum acceptable probability that $ORR \leq LRV$ given that a Go decision is made

Before reaching the planned sample size in a cohort, the posterior probabilities will be updated continuously after each patient or group of patients and will be used to determine, within each cohort, the predictive probability of eventually reaching a Stop decision at the planned sample size. If this predictive probability is $\geq 80\%$, then enrollment in that cohort may be stopped early for futility. Definitions of the decision boundaries can be found in [Section 7.6.6](#).

In general, Stop/Go and futility decision criteria are non-binding and may be regarded as guidance and information to be integrated with a full medical review of safety and efficacy data observed at the time of analysis in determining the next course of action.

No tests of statistical significance are planned.

Patients with missing ORR will be conservatively classified as non-responders for the primary analysis.

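### The synopsis puts the primary Go/Consider/Stop posterior on an undefined set of evaluable patients, which conflicts with the FAS and missing-as-non-response rule in Sections 7.5 and 7.6.1

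*Combined protocol and SAP*

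**What the plan says.** The Protocol Synopsis, under the analysis of the primary efficacy endpoint, says that within each cohort "the prior distribution will be updated with all available data from the evaluable patients to obtain the posterior distribution of the true ORR". Section 7.6.1 carries the same sentence without the restriction: "the prior distribution will be updated with all available data to obtain the posterior distribution of the true ORR". It then adds a rule that the synopsis lacks: "Patients with missing ORR will be conservatively classified as non-responders for the primary analysis".

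On the analysis population, the synopsis states "All efficacy analyses will be based on the FAS and will also be conducted on the mITT set and PPS for exploratory purposes", and Section 7.5 states "All efficacy analyses will be based on the FAS and will be conducted on the mITT set and PPS populations for exploratory purposes". Four sets are defined (FAS, mITT, safety, per-protocol). None is called evaluable. For CRC, both places limit the primary analysis to MSS and MSI-L patients.

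Three further provisions bear on the denominator. Section 4.2.3 allows no replacements. Section 7.6.6 counts enrolled patients for futility monitoring. Table 14 gives Go and Stop counts at the planned sample size, and Section 7.6.6 provides for recalculated boundaries only when a cohort is expanded.

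**The concern.** The posterior probabilities drive the Go/Consider/Stop call in each cohort, and the synopsis says that meeting the ORR endpoint would warrant a randomized Phase 2 trial in that tumour type. A patient who leaves before the first on-study scan at Week 9 has no response assessment. Section 7.6.1 keeps that patient as a failure. On its natural reading, the synopsis drops the patient. With no replacements, each dropped patient shrinks a denominator of 15 or 20.

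For a given number of responders, a smaller denominator can only raise the estimated ORR, so the synopsis version leans upward relative to the FAS version. The mITT definition expressly keeps patients who stop for clinical progression before the first scan, whereas an undefined evaluable set gives no such protection. In an open-label study, a denominator that can be read two ways leaves the choice open after responses have been seen.

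**Working it through.** **Inputs.** The prior is Beta(0.5, 0.5) (Section 7.6.1). The risk limits are 20% (false go) and 10% (false stop) (Section 7.6.1). LRV/TV are 10%/20% for CRC and OvC, 30%/40% for SCLC, and 15%/25% for TNBC and AML (Section 7.4). Planned numbers are 20, 20, 20, 15 and 15.

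**Formulas.** With r responders among n, the posterior is Beta(0.5 + r, 0.5 + n − r). Go is the smallest r with P(ORR ≤ LRV) ≤ 0.20. Stop is the largest r with P(ORR > TV) ≤ 0.10. The chance of each call at a given true ORR is an exact binomial tail.

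**Step 1: the plan's own figures.** At the planned numbers this reproduces Table 14 and the stated probabilities.

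| Cohort | Go / Stop | P(Go) at TV | P(Go) at LRV | P(Stop) at LRV |
|---|---|---|---|---|
| CRC, OvC (n = 20) | ≥4 / ≤1 | 58.9% (stated 59%) | 13.3% (13%) | 39.2% (39%) |
| SCLC (n = 20) | ≥8 / ≤5 | 58.4% (58%) | 22.8% (23%) | 41.6% (42%) |
| TNBC, AML (n = 15) | ≥4 / ≤1 | 53.9% (54%) | 17.7% (18%) | 31.9% (32%) |

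**Step 2: evaluable denominator, same limits.** Two assumptions are needed. The 20% and 10% limits are applied to the evaluable n, and each assessed patient responds with the stated true ORR.

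- *CRC/OvC, one unevaluable (n = 19).* P(ORR ≤ 10%) is 21.4% at 3/20 (Consider) and 19.0% at 3/19 (Go). The Go boundary falls from 4 to 3, and Stop stays at ≤1. P(Go | ORR = 10%) = P(X ≥ 3 | 19, 0.10) = 29.5%.
- *SCLC, one unevaluable (n = 19).* P(ORR > 40%) is 8.2% at 5/20 (Stop) and 11.0% at 5/19 (Consider). The Stop boundary falls from 5 to 4, and Go stays at ≥8. P(Stop | ORR = 30%) = P(X ≤ 4 | 19, 0.30) = 28.2%. P(Go | ORR = 30%) is 18.2%, below the stated 23%.
- *TNBC/AML, one unevaluable (n = 14).* 3/14 gives P(ORR ≤ 15%) = 23.5%, so Go stays at ≥4. Stop stays at ≤1.
- *TNBC/AML, two unevaluable (n = 13).* P(ORR ≤ 15%) is 27.4% at 3/15 and 19.8% at 3/13, so Go falls to 3. P(Go | ORR = 15%) = P(X ≥ 3 | 13, 0.15) = 30.8%.

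**Step 3: FAS, missing counted as non-response.** The denominators stay at 20 and 15, and Table 14 applies unchanged.

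- CRC/OvC, one missing: P(X ≥ 4 | 19, 0.10) = 11.5%.
- SCLC, one missing: P(X ≤ 5 | 19, 0.30) = 47.4% for Stop.
- TNBC/AML, two missing: P(X ≥ 4 | 13, 0.15) = 11.8%.

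**Step 4: fixed Table 14 counts.** If the counts are applied whatever the evaluable n, the call is the same as on the FAS. The reported estimate still moves. With 3 responders in CRC/OvC the posterior mean is 3.5/21 = 16.7% at 3/20 and 3.5/20 = 17.5% at 3/19. P(ORR > LRV) is 78.6% against 81.0%.

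**The case against.** The strongest reply is that the body of the protocol already settles the matter. Section 7.6.1 omits the qualifier and sets missing to non-response for the primary analysis, Section 7.5 and the synopsis both name the FAS, and futility counts enrolled patients. Only four words in the synopsis deviate. The criteria are also non-binding, and no significance tests are planned. All of this stands, and it lowers the severity. It does not remove the conflict, because the deviating words sit in the synopsis sentence that defines the primary posterior.

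A second reply is that Table 14 gives fixed counts at the planned sample size and that recalculation is foreseen only for expanded cohorts. This also stands: the effect on decisions depends on re-deriving boundaries at a smaller n, which the documents do not provide for. Still, the criteria are said to be derived from the two risk limits, so a reader with 19 patients could reasonably apply those limits to 19.

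Three stronger readings are tempting and are not supported:

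- *That one unevaluable patient changes the call in general.* It moves no boundary in TNBC or AML. Elsewhere the call changes only at one exact count (3 responders in CRC/OvC, 5 in SCLC) and by one category, never from Stop to Go.
- *That the protocol's false go risk doubles.* The protocol defines "20% false go risk: maximum acceptable probability that" the ORR is at or below the LRV given a Go. That posterior quantity is 19.0% at 3/19, within the cap. What rises is P(Go | ORR = LRV), and it more than doubles against the stated figure only in CRC/OvC (29.5/13.3 = 2.2). In TNBC/AML with two missing the ratio is 30.8/17.7 = 1.7.
- *That the size of the upward bias is known.* The documents give no rate of unevaluable patients and do not define the term.

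**Conclusion.** The inconsistency is real. The synopsis names an undefined denominator for the primary posterior, against the FAS basis stated in the synopsis and Section 7.5 and the missing-response rule in Section 7.6.1.

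Its possible effect on decisions is conditional on applying the posterior limits to the evaluable n. One unevaluable patient then lowers Go from 4 to 3 in CRC/OvC (P(Go | ORR = 10%) 29.5%, against 11.5% on the FAS and 13% stated). In SCLC one lowers Stop from 5 to 4 (P(Stop | ORR = 30%) 28.2%, against 47.4% on the FAS and 42% stated). Two in TNBC/AML lower Go from 4 to 3 (P(Go | ORR = 15%) 30.8%, against 11.8% on the FAS and 18% stated). With fixed Table 14 counts no call changes, but the reported ORR, credible interval and posterior probabilities still depend on which denominator is used.

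This is a should-fix: the right rule is already in the body text and the criteria are guidance, but the primary analysis should have one denominator.

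**What to change.** In the synopsis, delete the four words that separate "the prior distribution will be updated with all available data from the evaluable patients to obtain the posterior distribution of the true ORR" from "the prior distribution will be updated with all available data to obtain the posterior distribution of the true ORR". State there that the Go/Consider/Stop posterior uses the cohort's FAS (for CRC, the MSS and MSI-L patients only), with a missing response counted as non-response as in Section 7.6.1. If a posterior on evaluable patients is wanted, define the set and report it only as a sensitivity analysis. Carry the same wording into the SAP.

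The cost is a wording change. The one downside is that the estimated ORR may be slightly less favourable than on evaluable patients.

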For a full list of study procedures, including the timing of each procedure, please refer to [Section](#) and the Schedule of Assessments in [Table 8](#).

Estimated Study Duration:	Maximum study treatment duration is approximately 111 weeks (777 days; 2.13 years), during which the last galinpepimut-S administration would occur at 84 weeks (day 588 days; 1.61 years) – all time measurements assume t-zero the date of first galinpepimut-S administration, except specifically for safety, t-zero assumes the date of first GM-CSF administration (day -2 of the entire protocol schedule).
Efficacy Assessments:	Signal response for each a priori statistically defined clinical outcome (ORR per RECIST 1.1) for all solid tumor types or other appropriate instrument scales, such as attainment of morphologic CR in AML patients. In addition to RECIST 1.1, all scans will be read according to iRECIST immune response consensus guideline (Seymour et al, 2017) to ensure that patients are not discontinued from therapy due to the phenomenon of tumor “pseudoprogression”, and clinical decisions will be based on iRECIST (Hodi et al, 2016).
Exploratory Assessments:	ORR per iRECIST in patients in the solid tumor arms and the frequency (rate) of achievement of MRD negativity in patients in the AML arm will be evaluated as exploratory endpoints. All patients enrolled in the study will be followed and assessed for PFS and OS, according to the intent-to-treat (ITT) principle. Specifically for OS, patients who complete the protocol-specified study treatment period or patients who discontinue early will enter an off treatment follow-up period to assess OS, with regular assessments every 3 months until study closure (defined as up to 2 years and 6 weeks, i.e., 111 weeks after the first galinpepimut-S administration given to the last patient

enrolled into the study, which corresponds to 2 years after the first injection of pembrolizumab).

This study will also assess the effect of the study treatment on readouts of immunologic tests in PB samples, as well as presence and density of immune cell infiltrates within the tumor stroma (or BM in AML patients) using at least one post-therapy tumor biopsy (and comparing the findings with those at baseline, i.e., prior to initiation of treatment). Details are provided in [Section 6.3](#).

Safety Assessments:

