Given a sample size of 20 patients in SCLC group, where TV = 40% and LRV = 30%, the decision criteria are as follows: Go if ≥ 8 responses observed (40%); Stop if ≤ 5 responses observed (20%). With these criteria, there is a 58% probability of a Go decision and 13% probability of a Stop decision if the true ORR is 40%, and there is a 23% probability of a Go decision and 42% probability of a Stop decision if the true ORR is 30%.

TNBC

Given a sample size of 15 patients in the triple negative breast cancer group, where TV=25% and LRV=15%, the decision

criteria are as follows: Go if ≥ 4 responses observed (27%); Stop if ≤ 1 responses observed (7%). With these criteria, there is a 54% probability of a Go decision and 8% probability of a Stop decision if the true ORR is 25%, and there is a 18% probability of a Go decision and 32% probability of a Stop decision if the true ORR is 15%.

AML

The same sample size, TV, LRV, decision criteria, and probability statements as the TNBC group apply.

General Considerations

Data will be summarized and/or analyzed by cohort. Safety and demographic data will be summarized using standard tabulations and listings. Continuous variables will be summarized using descriptive statistics such as mean, standard deviation, median, minimum value, and maximum value. Continuous variables may be summarized by a clinically relevant discretization, as appropriate. Categorical variables will be summarized using frequency counts and percentages. Time-to-event data will be summarized using the Kaplan-Meier method. All time to event endpoints are measured from day of enrollment (Day-2 pretreatment baseline visit). Where appropriate, 95% confidence intervals around point estimates will be presented, and estimates of the median and other quantiles, as well as individual time points (e.g., 3-month, 6-month, and 12-month rates), will be produced. Data will be provided in data listings.

Objective response rate will be reported with category counts, percentage and 95% confidence interval. Duration of response (DOR), TTR, and OS will be evaluated using Kaplan-Meier estimates and curves will be generated based on these estimates.

SELLAS Life Sciences Group

Protocol: SLS17-201/MK3475-770 Protocol v1.1 (Amendment 1.0)

Galinpepimut-S

12 April 2019

Date of Protocol 12 April 2019
Amendment:

List of Abbreviations

Abbreviation	Definition
aa	amino acids
AE	adverse event

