6.8.2. Tumor Imaging During the Study

For solid tumors only, the first on-study imaging assessment should be performed at Week 9 (Day 1 \pm 7 days) from the date of enrollment. Subsequent tumor imaging should be performed at Weeks 18, 27, 36, 45, 54, 63, 72, and 84 (Day 1 \pm 7 days) or more frequently if clinically indicated. Imaging timing should follow calendar days and should not be adjusted for delays in cycle starts. Imaging should continue to be performed until disease progression is identified by the investigator.

Objective response should be confirmed by a repeat imaging assessment. Tumor imaging to confirm PR or CR should be performed at least 4 weeks after the first indication of a response is observed. Patients will then return to regular scheduled imaging, starting with the next scheduled imaging time point. Patients who receive additional imaging for confirmation do not need to undergo the next scheduled tumor imaging if it is less than 4 weeks later; tumor imaging may resume at the subsequent scheduled imaging time point.

Per iRECIST ([Section 6.8.5](#)), disease progression should be confirmed by the site 4 to 8 weeks after.

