7.2. Secondary Efficacy Endpoints

The secondary efficacy endpoints are TTR, time to next treatment and DOR.

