7.6.2. Analysis of Secondary Efficacy Endpoints

Secondary endpoints will be summarized by cohort using descriptive statistics. No formal tests of hypotheses are planned. Duration of response (DOR) and TTR will be evaluated using Kaplan-Meier estimates and curves will be generated based on these estimates.

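### Read literally, the synopsis starts the duration-of-response clock at enrollment, so each responder's DOR includes that patient's own time to response (nominally about 9 weeks for a response first seen at the first scheduled assessment)

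*Combined protocol and SAP*

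**What the plan says.** The synopsis, under Statistical Methods, General Considerations, sets the origin: "All time to event endpoints are measured from day of enrollment (Day-2 pretreatment baseline visit". The next paragraph applies Kaplan-Meier methods to DOR: "Duration of response (DOR), TTR, and OS will be evaluated using" Kaplan-Meier estimates. The same General Considerations text plans landmark rates, with 3, 6 and 12 months as examples.

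In the body, DOR is named but not defined:

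- Section 2.2 lists it as a secondary objective.
- Section 7.2: "The secondary efficacy endpoints are TTR, time to next treatment and DOR".
- Section 7.6.2: "Duration of response (DOR) and TTR will be evaluated using Kaplan-Meier estimates".

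None of these gives a start event, an end event or a censoring rule. Section 7.6 repeats most of the synopsis paragraph without the origin sentence and refers to the SAP for data conventions.

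The synopsis entry on Estimated Study Duration gives a second general origin: "all time measurements assume t-zero the date of first galinpepimut-S administration". Its only exception is safety, which Section 7.6.4 repeats.

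On timing, Section 6.8.2 says that "the first on-study imaging assessment should be performed at Week 9", with a window of 7 days either side, counted "7 days) from the date of enrollment". The next scheduled scan is at Week 18. Table 8 also places the first on-treatment marrow for AML at Week 9.

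**The concern.** DOR is meant to describe how long a response lasts once it has been achieved. If the clock starts at enrollment, the quantity estimated among responders is time from enrollment to progression or death. TTR and DOR then share a start and overlap, and no responder can have an event before the response occurs, so the early part of the curve is event-free by construction.

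This matters because the secondary hypothesis in the synopsis is that the combination may improve on pembrolizumab monotherapy in TTR, time to next treatment and DOR. The trial has no control arm, so any such reading is against outside data. If the outside DOR is counted from first response, the comparison favours the combination. Six of the nine weeks before the first scan also precede the first pembrolizumab dose, which is given at Week 6.

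DOR can carry some weight in decisions. Section 7.4 lets secondary endpoints guide the next step when a cohort falls in the Consider zone, which Tables 11 to 13 give a probability of 29% to 50% at the listed response rates. Sections 7.4 and 7.6.6 also let the sponsor add about 10 patients to a cohort to obtain more data on primary or secondary endpoints.

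**Working it through.** The plan states no DOR figure, so there is nothing to reproduce. The check is the size of the offset.

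**Formula.** Let T0 be enrollment, R the first documented response, and E the end of response (or censoring).

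- DOR as written = E − T0
- DOR from response = E − R
- Excess = R − T0, which is that patient's TTR. It is the same whether E is an event or a censoring time.

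**Excess for a response first seen at the first scheduled assessment** (1 month = 30.4375 days):

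| Reading of the schedule | Nominal | With the 7-day window |
|---|---|---|
| Week 9 counted from enrollment (Section 6.8.2) | 63 days = 9.0 weeks = 2.07 months | 56 to 70 days = 8.0 to 10.0 weeks |
| Week 9 counted from first dose, enrollment Day -2 | 65 days = 9.3 weeks | 58 to 72 days = 8.3 to 10.3 weeks |
| Week 9 counted from first dose, enrollment Day -3 | 66 days = 9.4 weeks | 59 to 73 days = 8.4 to 10.4 weeks |

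If the clock instead starts at the first galinpepimut-S dose and Week 9 is also counted from that dose, the excess is again 9.0 weeks nominal. Choosing between the two stated origins does not remove it.

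**Later responses.** First seen at Week 18: 18 × 7 / 30.4375 = 4.1 months. First seen at Week 27: 27 × 7 / 30.4375 = 6.2 months.

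**Effect on a reported DOR.** The documents give no expected DOR, so the true values below are assumptions, with every response first seen at Week 9:

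| Assumed true DOR | Reported | Overstatement |
|---|---|---|
| 3 months | 3 + 2.07 = 5.1 months | 2.07 / 3 = +69% |
| 6 months | 6 + 2.07 = 8.1 months | 2.07 / 6 = +34% |
| 12 months | 12 + 2.07 = 14.1 months | 2.07 / 12 = +17% |

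**Effect on the 3-month rate, solid tumors.** Section 6.8.2 asks for confirmation at least 4 weeks after response is first seen. A Week 9 response that is confirmed is therefore still present at Week 13 or later: 13 × 7 / 30.4375 = 2.99 months from enrollment. With the earliest in-window scan, at week 8, this becomes week 12, or 2.76 months. Responses first seen at Week 18 or later have passed 3 months before they begin. A 3-month DOR rate on this clock would be close to 100% whatever the treatment does.

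**The case against.** The strongest reply is that this is loose drafting and not a planned analysis. The sentence is a general one in the synopsis, the term duration of response itself implies a start at response, Section 7.6 leaves the sentence out, and the SAP may define DOR in the usual way. This limits the certainty: one cannot say that the analysis will be run from enrollment, or that the SAP shares the fault. It does not remove the point. The synopsis sentence covers all such endpoints, DOR is listed immediately after it, and the authors wrote an exception for safety but none for DOR. A conventional SAP definition would contradict the protocol as it stands.

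A reader might infer a floor of 9 weeks for every responder. Section 6.8.2 does not support that. The window permits a first scan at 8 weeks, and extra imaging is allowed when clinically warranted, so an earlier response could in principle be recorded.

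A reader might also infer that the cohort decisions are biased. They are not directly affected: the Go, Stop and futility criteria in Section 7.6.6 use response counts only and are non-binding, and Section 7.6.2 plans no hypothesis test on secondary endpoints. The documents give no historical DOR figure and no method for a DOR comparison, so the bias against outside data depends on that DOR being counted from response.

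Finally, TTR and data listings are also planned, so the offset could be removed patient by patient. That helps a careful reader of the report, but the headline DOR would still be wrong.

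**Conclusion.** The point stands as a fault in a stated rule, of moderate importance. Followed literally, the protocol yields TTR plus the true duration of response for each responder. The excess is nominally about 9 weeks (8 to 10 with the window) for a response first seen at the first scheduled assessment and about 18 weeks for one first seen at Week 18. It could be smaller if an unscheduled scan shows response earlier. The nominal Week 9 figure applies equally to the AML arm through the marrow schedule.

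The percentages rest on assumed true durations and on response at Week 9. The whole point rests on the supplied text, because the separate SAP could not be checked. DOR is descriptive, so the effect falls on interpretation and on any informal use in the Consider zone or in cohort expansion. The primary response-rate decisions are untouched.

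**What to change.** 1. Limit the enrollment origin in the synopsis to OS, PFS, TTR and time to next treatment.
2. Define DOR in responders only, from first documented response (CR or PR later confirmed in solid tumors; CR/CRi/CRp in AML) to progression or relapse, or death.
3. Add a censoring rule, for example at the last evaluable disease assessment for responders without an event, and say how new anticancer therapy is handled.
4. Put the same definition in Section 7.6.2 and make sure the SAP matches.
5. Use one t-zero in both synopsis entries, and reconcile the baseline/enrollment visit, which is Day -2 in the synopsis but Day -3 in Section 6, Section 6.1.1 and Table 8.

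The cost is a few sentences of text, with no change to visits, enrollment or sample size. The reported DOR will be less favourable, by each responder's TTR.
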